#### 7.4 Special Warnings and Precautions for Use

#### 7.4.1 Hepatic Impairment

Subjects with cirrhosis, abnormal synthetic liver function and history or presence of decompensated liver disease will not be enrolled to the study. Liver function tests will be monitored during treatment and criteria for discontinuing treatment should be followed (see Stopping Rules, Section 7.5.2 and 7.5.3)

#### 7.4.2 Renal Impairment

Subjects with renal dysfunction with eGFR < 45 ml/min using the MDRD formula will not be enrolled to the study. GFR will be monitored during treatment and discontinuation may be required.

For a detailed description of special warnings and precautions refer to the current IB.

# 7.5 Stopping Criteria

A subject may discontinue participation in the study at any time for any reason (e.g., AE, consent withdrawal). The Investigator and/or Sponsor can withdraw a subject from the study at any time for any reason (e.g., protocol deviation, noncompliance, AE).

#### 7.5.1 Pregnancy

Currently available data from non-clinical studies is not sufficient to rule out a potential risk on pregnancy and adequate and well-controlled studies have not been conducted in pregnant or breastfeeding women to inform drug-associated risks. Furthermore, the study may require procedures that are associated with heightened risks in pregnancy (i.e. biopsy). Hence, pregnancy should be avoided during study and 1 month after treatment discontinuation.

Any subject who becomes pregnant during the study must not receive additional doses of the study drug and will be withdrawn from the study.

All females of childbearing potential should practice a highly effective method of reliable contraception at least 1 month prior to randomization, throughout the study period and for 1 month after treatment discontinuation.

A woman is considered of childbearing potential if fertile, following menarche and until becoming post-menopausal unless permanently sterile. Permanent sterilisation methods include hysterectomy, bilateral salpingectomy and bilateral oophorectomy. A postmenopausal state is defined as no menses for 12 months without an alternative medical cause.

	_

For detailed description of non-clinical reproduction toxicity studies refer to the current IB.

#### 7.5.2 **DILI Monitoring and Stopping Rules**

Hepatocellular and cholestatic DILI should be monitored during the study and subjects should be educated to recognize symptoms and seek immediate medical care.

When the Investigator or site personnel, or the Medical Monitor becomes aware of a case of suspected DILI, or discontinuation due to suspected DILI, all relevant parties (Investigator, Medical Monitor, Sponsor) are to be notified immediately.

[figure not shown]
#### 7.5.2.1 **Hepatocellular DILI:**

Guidelines refer to subjects with Normal Baseline transaminase and subjects with Elevated Baseline transaminase.

Definition of Baseline transaminase (ALT and AST):

• Baseline value is the average of values from screening and baseline visits (from the central laboratory)

A subject is defined to have an Elevated Baseline when the average values from screening and baseline visits of either ALT and/or AST are ≥1.5 x ULN

\*A "new baseline": Transaminase levels might decline during the study. If the average transaminase value from the two visits prior to the suspected DILI event is lower than the original elevated baseline value (average from screening and baseline visits), this value should be set as the new baseline. If the new baseline is within the normal range, guidelines for normal baseline values should be followed.

For subjects under close observation, liver tests should be repeated within 2-5 days and an assessment for hepatic symptoms should be performed. The frequency of subsequent testing (weekly or biweekly) should be determined based on the subject's clinical condition.

[figure not shown]
## If close monitoring is not possible, study drug should be discontinued.

If a subject meets the discontinuation criterion, continue monitoring until the laboratory elevations/symptoms have resolved or stabilized, or until a determination of a cause unrelated to the study drug is made.

#### **7.5.2.1.1** DILI Workup

#### Confirmation

An increase of serum ALT or AST to >3xULN (if normal at baseline) or increase in serum ALT or AST to  $\ge 2x$  baseline (if abnormal at baseline) should be followed by repeat testing within 48 to 72 hours of ALT, AST, ALP, TBL, CPK and INR to confirm the abnormalities and to determine if they are increasing or decreasing. There also should be inquiry made about symptoms. Blood samples for Aramchol PK should also be obtained.

If close monitoring is not possible, study drug should be immediately discontinued.

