# 7.5.2.2 Cholestatic DILI

# Table 1: Monitoring and stopping rules for cholestatic DILI

EVENT	ALT/AST levels	TOTAL BILIRUBIN	ACTION
Doubling of conjugated or direct bilirubin (CB or DB) - within normal values	Mild elevations*	Mild elevations*	Perform close monitoring
Doubling of conjugated or direct bilirubin (CB or DB) – above normal values	Mild elevations*	Mild elevations*	Interrupt the treatment, closely monitor the patient and initiate potential DILI evaluation.  Treatment can only be initiated if an alternate etiology for liver enzyme elevation is established.
ALP/GGT ≥ 2xULN (for normal baseline)			Perform close monitoring

[figure not shown]
EVENT	ALT/AST levels	TOTAL BILIRUBIN	ACTION
ALP/GGT ≥2x baseline and> ULN (for elevated baseline)			
ALP/GGT ≥ 2xULN (for normal baseline)	Mild elevations*	Mild elevations*	Interrupt the treatment, closely monitor the patient and initiate potential DILI evaluation.
ALP/GGT ≥2x baseline and> ULN (for elevated baseline)			Treatment can only be initiated if an alternate etiology for liver enzyme elevation is established.
Total bilirubin elevation and symptoms consistent with clinical hepatitis (right upper quadrant pain or tenderness, jaundice, rash,	Any magnitude	2 X ULN	Discontinue the treatment, closely monitor the patient and initiate potential DILI evaluation.
etc)			Treatment can only be initiated if an alternate etiology for liver enzyme elevation is established. If no cause is found, re-challenge should not be initiated.

\* Mild elevation refers to CTCAE grade 1:

- ALT/AST: >ULN 3 x ULN if baseline was normal; 1.5 3.0 x baseline if baseline was abnormal
- Total bilirubin: >ULN 1.5 x ULN if baseline was normal; > 1 1.5 x baseline if baseline was abnormal

If after re-challenge, a patient experiences DILI (i.e., recurrent elevations of total bilirubin, ALT, or AST), irrespective of the magnitude of liver enzymes elevation), the study drug should be discontinued permanently.

[figure not shown]

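### The DILI rules do not use one consistent boundary between a normal and an elevated transaminase baseline, so the retest and interruption conditions are ambiguous for baselines above ULN and below 1.5 x ULN

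*Combined protocol and SAP*

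**What the plan says.** Four pieces of text bear on the point.

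- **Section 7.5.2.1, classes.** The hepatocellular guidance works with two groups: "Guidelines refer to subjects with Normal Baseline transaminase and subjects with Elevated Baseline transaminase". A subject belongs to the elevated group when the average of the screening and baseline values "of either ALT and/or AST are ≥1.5 x ULN". The visible text gives no upper limit for the normal group.
- **Section 7.5.2.1, new baseline.** If transaminases decline during the study, the average of the two visits before the suspected event replaces an original elevated baseline. Then: "If the new baseline is within the normal range, guidelines for normal baseline values should be followed".
- **Section 7.5.2.1.1, Confirmation.** One trigger is "An increase of serum ALT or AST to >3xULN (if normal at baseline". The other is a rise to at least twice baseline, and its condition reads "if abnormal at baseline) should be followed by repeat testing within 48 to 72 hours". The defined word, elevated, is not used here, and abnormal is not defined.
- **Section 7.5.2.2, Table 1 and footnote.** A mild ALT/AST elevation runs from above ULN to 3 x ULN "if baseline was normal; 1.5 3.0 x baseline if baseline was abnormal"; I read the second part as a range of 1.5 to 3.0 times baseline. Where ALP or GGT reaches its trigger and both the ALT/AST and total bilirubin cells show mild elevations, the action is: "Interrupt the treatment, closely monitor the patient and initiate potential DILI evaluation". The same ALP/GGT event with those cells blank calls for close monitoring only.

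Exclusion criterion 4 in Section 6.2 removes subjects only when ALT or AST exceeds 5 x ULN, so a baseline between 1.0 and 1.5 x ULN is admissible.

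**The concern.** A baseline of 1.2 x ULN is not elevated under the 1.5 x ULN definition, yet it is not within the normal range either. The visible text does not say which rule governs it. The choice matters in two places: whether a raised ALT or AST calls for confirmatory testing within 48 to 72 hours with a PK sample, and whether a cholestatic signal leads to interruption or to close monitoring.

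About 200 sites are planned for the randomized part. If the text admits two readings, retesting and interruption may depend on the reader rather than on the laboratory result. What is at stake is safety follow-up and consistent handling of study drug. No sample size, power or alpha figure depends on it.

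**Working it through.** The plan states no figure to reproduce. I apply its own multipliers to a baseline *b*, in multiples of ULN.

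**Formulas**
- Retest trigger (Section 7.5.2.1.1): normal rule >3.0; abnormal rule ≥2*b*; gap 3 − 2*b*.
- Mild ALT/AST window (Table 1 footnote): normal rule >1.0 to 3.0; abnormal rule 1.5*b* to 3.0*b*.

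| *b* | Retest, normal | Retest, abnormal | Gap | Mild, normal | Mild, abnormal |
|---|---|---|---|---|---|
| 1.01 | >3.0 | ≥2.02 | 0.98 | >1.0–3.0 | 1.52–3.03 |
| 1.2 | >3.0 | ≥2.40 | 0.60 | >1.0–3.0 | 1.80–3.60 |
| 1.4 | >3.0 | ≥2.80 | 0.20 | >1.0–3.0 | 2.10–4.20 |
| 1.5 | >3.0 | ≥3.00 | 0.00 | >1.0–3.0 | 2.25–4.50 |

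**Retest example.** Baseline 1.2, ALT now 2.7. Since 2.7 ≥ 2 × 1.2 = 2.4, the abnormal rule calls for a retest. Since 2.7 < 3.0, the normal rule does not.

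**New-baseline example.** One subject enters at 1.2. Another enters at 2.0 and falls to 1.2. The first is not elevated by the 1.5 definition; if treated as normal, the trigger is >3.0. The second does not meet the stated condition for the normal guidelines, so by implication the baseline-multiple rule continues from the lower value, with a trigger of ≥2.4. The working baseline is the same, but the rules can differ.

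The new-baseline sentence also creates a step at ULN. A lowered baseline of 1.01 gives a trigger of ≥2.02, while one at or below 1.0 gives >3.0.

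**Table 1 example.** Baseline ALT 1.2, current ALT 1.5, ALP or GGT at its trigger, bilirubin mildly elevated.
- Baseline counted as normal: 1.5 lies within >1.0 to 3.0, so ALT is mildly elevated and the interruption row is met.
- Baseline counted as abnormal: 1.5 / 1.2 = 1.25 times baseline, below the 1.5 floor (1.5 × 1.2 = 1.80 x ULN). ALT is not mildly elevated, and the interruption row is not met.

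The example takes the ALT/AST and bilirubin cells as joint conditions, as the table layout suggests.

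**Testing each candidate boundary against the text**
- *Normal means below 1.5 x ULN.* This fits the definition and the retest rule. It does not fit the new-baseline sentence, which requires the normal range. In the footnote, a subject stable at 1.2 x ULN would already count as mildly elevated with no change from baseline.
- *Normal means at or below ULN.* This fits the new-baseline sentence and the footnote. It leaves a baseline of 1.0 to 1.5 x ULN abnormal but not elevated, in guidance that names only normal and elevated groups.

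**The case against.** The best defence is that Section 7.5.2.1.1 sits under Section 7.5.2.1, which names two classes, so abnormal should be read as elevated. A subject entering at 1.2 x ULN then has one trigger, >3.0 x ULN. The numbers support this: 2 × 1.5 = 3.0, so the two retest rules join exactly at the defined boundary. I accept that this settles the retest rule taken alone for a baseline measured at entry. It does not settle the new-baseline sentence or the footnote.

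The new-baseline sentence applies only to subjects who began elevated. Treating them differently from subjects who entered at the same level could be deliberate, and Table 1 is a separate cholestatic rule set tied to CTCAE grade 1. Both points are fair, but the protocol states neither intention.

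A reader might infer more than the text supports:
- *That every subject at 1.0–1.5 x ULN faces two conflicting triggers.* The text is ambiguous for them; it does not impose both rules on one subject.
- *That ALT and ALP alone decide interruption in Table 1.* The row also lists mildly elevated total bilirubin.
- *That hepatocellular interruption thresholds differ too.* They are not shown in the public copy, and their absence is not a fault in the plan.
- *That such baselines are common, or that sites do act differently.* The documents give no frequency, and divergence between sites is a possibility, not an observed fact.

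**Conclusion.** The concern holds as an internal inconsistency. The definition of an elevated baseline, the new-baseline rule and the Table 1 footnote cannot all be met by one boundary, and the retest rule uses an undefined term.

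For baselines above ULN and below 1.5 x ULN, the two readings of the retest trigger differ by up to about 1 x ULN just above ULN, by 0.6 x ULN at a baseline of 1.2, and by nothing at 1.5. In the cholestatic rules, the choice of reading can decide whether the interruption row is met.

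This rests on two assumptions: that a lowered baseline still above ULN stays on the baseline-multiple rule, which the text implies but does not state; and that the two mild-elevation cells in Table 1 are joint conditions. Material not shown may define the normal group, but a 1.5 x ULN limit there would still sit badly with the new-baseline sentence and the footnote. Which boundary is clinically right is not judged here.

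**What to change.** Reconcile the passages. Define one term and one boundary for a normal versus an elevated transaminase baseline. Use it in Section 7.5.2.1 (both the definition and the new-baseline rule), in the Confirmation text of Section 7.5.2.1.1 and in the Table 1 footnote. If a different baseline convention is intended in any of these places, say so there, and state which rule governs a baseline above ULN and below 1.5 x ULN. The sponsor decides which boundary applies. The cost is protocol wording only.

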#### Close Observation

- Repeating liver enzyme and serum bilirubin tests two or three times weekly. Frequency
  of retesting can decrease to once a week or less if abnormalities stabilize or study drug
  has been discontinued and the subject is asymptomatic.
- Obtaining a more detailed history of symptoms and prior or concurrent diseases.
- Obtaining a history of concomitant drug use (including nonprescription medications and herbal and dietary supplement preparations), alcohol use, recreational drug use, and special diets.
- Ruling out acute viral hepatitis types A, B, C, D, and E; autoimmune or alcoholic hepatitis; hypoxic/ischemic hepatopathy; and biliary tract disease.
- Obtaining a history of exposure to environmental chemical agents.
- Obtaining additional tests to evaluate liver function, as appropriate (e.g., INR, direct bilirubin). In case of discontinuation, study drug can be restarted only if another etiology is identified and liver enzymes have returned to normal levels.

If after re-challenge, a subject experiences DILI (i.e., recurrent elevations of total bilirubin, ALT, or AST), irrespective of the magnitude of liver enzymes elevation, the study drug should be discontinued permanently.

# 7.5.2.2 Cholestatic DILI

# Table 1: Monitoring and stopping rules for cholestatic DILI

EVENT	ALT/AST levels	TOTAL BILIRUBIN	ACTION
Doubling of conjugated or direct bilirubin (CB or DB) - within normal values	Mild elevations*	Mild elevations*	Perform close monitoring
Doubling of conjugated or direct bilirubin (CB or DB) – above normal values	Mild elevations*	Mild elevations*	Interrupt the treatment, closely monitor the patient and initiate potential DILI evaluation.  Treatment can only be initiated if an alternate etiology for liver enzyme elevation is established.
ALP/GGT ≥ 2xULN (for normal baseline)			Perform close monitoring

[figure not shown]
EVENT	ALT/AST levels	TOTAL BILIRUBIN	ACTION
ALP/GGT ≥2x baseline and> ULN (for elevated baseline)			
ALP/GGT ≥ 2xULN (for normal baseline)	Mild elevations*	Mild elevations*	Interrupt the treatment, closely monitor the patient and initiate potential DILI evaluation.
ALP/GGT ≥2x baseline and> ULN (for elevated baseline)			Treatment can only be initiated if an alternate etiology for liver enzyme elevation is established.
Total bilirubin elevation and symptoms consistent with clinical hepatitis (right upper quadrant pain or tenderness, jaundice, rash,	Any magnitude	2 X ULN	Discontinue the treatment, closely monitor the patient and initiate potential DILI evaluation.
etc)			Treatment can only be initiated if an alternate etiology for liver enzyme elevation is established. If no cause is found, re-challenge should not be initiated.

\* Mild elevation refers to CTCAE grade 1:

- ALT/AST: >ULN 3 x ULN if baseline was normal; 1.5 3.0 x baseline if baseline was abnormal
- Total bilirubin: >ULN 1.5 x ULN if baseline was normal; > 1 1.5 x baseline if baseline was abnormal

If after re-challenge, a patient experiences DILI (i.e., recurrent elevations of total bilirubin, ALT, or AST), irrespective of the magnitude of liver enzymes elevation), the study drug should be discontinued permanently.

[figure not shown]

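### Table 1 caps its two interruption rows at mild elevations, so a worse first cholestatic result can call for a weaker action

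*Combined protocol and SAP*

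**What the plan says.** Section 7.5.2.2, Table 1, links each cholestatic event to an action through an ALT/AST column and a total bilirubin column.

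- **Two rows interrupt treatment.** One is headed "Doubling of conjugated or direct bilirubin (CB or DB) – above normal values". The other covers ALP/GGT at or above 2×ULN (normal baseline), or at or above 2× baseline and over ULN (elevated baseline). Both ask for mild elevations in both laboratory columns.
- **The footnote bounds mild.** It states "Mild elevation refers to CTCAE grade 1" and gives the limits as "ALT/AST: >ULN 3 x ULN if baseline was normal; 1.5 3.0 x baseline if baseline was abnormal" and "Total bilirubin: >ULN 1.5 x ULN if baseline was normal; > 1 1.5 x baseline if baseline was abnormal". The range dashes are lost in the text copy, but a CTCAE grade has an upper limit in any case.
- **A separate ALP/GGT row**, with both laboratory cells blank, asks only for close monitoring.
- **The last row discontinues treatment.** Its event is "Total bilirubin elevation and symptoms consistent with clinical hepatitis (right upper quadrant pain or tenderness, jaundice, rash" and similar signs), with total bilirubin at 2×ULN. Its ALT/AST cell reads "Any magnitude".

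The sentence under the table that disregards the size of the elevation applies only after re-challenge.

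**The concern.** A stopping rule should not become more lenient as the laboratory picture worsens. Because the interruption rows are tied to a band rather than a floor, a subject with a triggering ALP/GGT or direct bilirubin whose total bilirubin has passed the top of the band leaves the interruption row without entering a stronger one. The last row shows that the table has wording for an uncapped column; these two rows do not use it.

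The gap concerns the first triggering result. A subject already interrupted at a mild value stays off drug, because restarting requires another established cause. A first result above the band is plausible, since visits become 12 weeks apart after week 12 (Section 8.1). The placebo-controlled part plans 2000 subjects at about 200 sites, treated for up to 7 years. What is at stake is delayed or inconsistent interruption between sites, not a subject whom nobody is watching.

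**Working it through.** The plan gives no figure to reproduce here. The check applies Table 1 literally, as a decision rule.

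**Inputs from Table 1 and its footnote (normal baseline, in multiples of ULN)**
- Mild ALT/AST: 1 < ALT ≤ 3. Mild total bilirubin (TB): 1 < TB ≤ 1.5.
- Trigger D: direct bilirubin doubled above normal. Trigger A: ALP/GGT ≥ 2.
- Discontinuation row: the bilirubin cell prints no operator and is read as TB ≥ 2 (assumption).
- Blank cells in the ALP/GGT monitoring row: read both as any value and as normal values.

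**Rule**
- Interrupt if (D or A) and 1 < ALT ≤ 3 and 1 < TB ≤ 1.5.
- Discontinue if symptoms are present and TB ≥ 2.
- Monitor if A is present and blank cells mean any value.
- Otherwise no row applies.

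**Illustrative values.** ALT = 2; TB = 1.3, 1.8 or 2.5. Each TB level has 2 triggers × 2 symptom states = 4 cells.

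| TB (×ULN) | Trigger | No symptoms | Symptoms |
|---|---|---|---|
| 1.3 | D | interrupt | interrupt |
| 1.3 | A | interrupt | interrupt |
| 1.8 | D | no row | no row |
| 1.8 | A | monitor, or no row | monitor, or no row |
| 2.5 | D | no row | discontinue |
| 2.5 | A | monitor, or no row | discontinue |

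**Cells below interruption**
- TB 1.3: 0 of 4.
- TB 1.8: 4 of 4. Symptoms do not help, because the last row starts at 2×ULN.
- TB 2.5: 2 of 4.
- Above the mild range: 4 + 2 = 6 of 8. If blanks mean any value, these are 3 monitoring and 3 no row; if blanks mean normal values, all 6 are no row.

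The pattern holds at other values. With ALT at 2×ULN and no symptoms, TB of 1.2×ULN interrupts and TB of 1.8 or 3×ULN does not, also when both triggers are present.

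**Variations**
- *Jaundice.* It is a listed symptom. If everyone at TB 2.5 is counted as jaundiced, those 2 cells become discontinuation: 4 + 0 = 4 of 8.
- *Abnormal bilirubin baseline, assumed 1.4×ULN.* The mild range ends at 1.5 × 1.4 = 2.1×ULN. TB 1.8 then gives 0 of 4 and TB 2.5 gives 2 of 4: 2 of 8 in total.
- *ALT at 4×ULN, normal baseline.* Even TB 1.3 gives 4 of 4 below interruption within Table 1. Section 7.5.2.1 may already cover these subjects.
- *Normal ALT (0.9×ULN).* TB 1.3, 1.8 and 2.5 give 4 of 4, 4 of 4 and 2 of 4.

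**With the cap removed.** The rule becomes: interrupt if (D or A) and both ALT/AST and TB are at least mildly raised. For ALT 2 and a normal baseline, all TB 1.8 cells interrupt, and TB 2.5 cells interrupt or, with symptoms, discontinue: 0 of 8. The abnormal-baseline case also becomes 0 of 8, and the ALT 4×ULN case 0 of 4. The normal-ALT counts do not change.

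**The case against.** The strongest objection is that a subject is governed by all of Section 7.5.2, and much of it cannot be read. Section 7.5.2.1 announces guidelines by baseline transaminase and then says "If a subject meets the discontinuation criterion, continue monitoring until the laboratory" abnormalities settle, but the criterion itself is not visible; nor is Table 2. Those thresholds may use bilirubin as well as ALT/AST, since the workup in 7.5.2.1.1 repeats both. For abnormal baselines, its confirmation trigger of 2× baseline lies inside the mild ALT/AST band, so the pathways overlap. This stands as a limit on the conclusion. It does not remove the core case: with a normal baseline and ALT at 2×ULN, the subject is below the visible confirmation trigger of more than 3×ULN, and Table 1 is where the plan places cholestatic injury.

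Second, mild was probably meant as an entry threshold, and few investigators would keep dosing because results are worse. That is likely true of intent, but the footnote defines a range, and about 200 sites should not each have to infer the intended rule.

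Third, other safeguards exist: withdrawal at the investigator's discretion (7.5), immediate notification (7.5.2), stopping when close monitoring is impossible (7.5.2.1 and 7.5.2.1.1), "Repeating liver enzyme and serum bilirubin tests two or three times weekly" (7.5.2.1.1), laboratory alerts (9.9.2), and hepatic adjudication and the DMC (Section 10). They make an unobserved case unlikely. None of them states that drug is interrupted at these values.

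Fourth, the counts come from chosen values with equal weights. This is correct; they show the direction of the rule and do not measure its impact.

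**Conclusion.** The concern holds for Table 1 read literally, for a first triggering result. At ALT 2×ULN with a normal baseline, raising total bilirubin from 1.3 to 1.8×ULN moves all 4 cells from interruption to monitoring or no row, with or without symptoms. That result does not depend on how the blank cells are read or on whether jaundice counts as a symptom.

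Across 1.8 and 2.5×ULN, 6 of 8 cells fall short of interruption. The count is 4 of 8 if everyone at 2.5×ULN is jaundiced, and 2 of 8 for an assumed bilirubin baseline of 1.4×ULN. The conclusion rests on reading the last row as at least 2×ULN, and says nothing about what the unseen 7.5.2.1 thresholds would add. The documents do not allow the number of subjects affected to be estimated. This should be corrected because a stated safety rule weakens as the result worsens.

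**What to change.** In the two interruption rows of Table 1, replace the mild-elevation entries with mild or greater elevations (CTCAE grade 1 or above), in both the ALT/AST and the total bilirubin column. Leave the discontinuation row as it is, so that it still governs symptomatic bilirubin at 2×ULN or more.

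While editing, the sponsor should compare the two rows with the full 7.5.2.1 criteria, so that a result assigned to discontinuation there is not downgraded to interruption here. The change does not affect subjects whose ALT/AST is normal; if interruption is also wanted for them, that is a separate decision.

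The cost is one revised table in the next amendment, a memo to sites, and possibly a few more treatment interruptions. No visits or tests are added.
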